## 2.0 STUDY OBJECTIVES AND ENDPOINTS

### 2.1 Primary Objective

To compare (using a reader study) the sensitivity and specificity of acoustic angiography to the sensitivity and specificity of conventional b-mode ultrasound in evaluation of breast lesions

### 2.2 Secondary Objectives

2.2.1 To compare the area under the curve (AUC) of acoustic angiography to the AUC of the b-mode ultrasound

2.2.2 To compare radiologist preference of acoustic angiography to conventional b-mode ultrasound for each lesion characteristic (shape, margins and vascularity)

2.2.3 To quantify vessel tortuosity metrics for the acoustic angiograph images, and to use these metrics to develop a model for predicting malignancy (a model-based malignancy score)

2.2.4 To compare the model-based malignancy score to the acoustic angiography reader study

### 2.3 Primary Endpoint

Sensitivity and specificity for our study is defined as the ability of readers (radiologists) to use the acoustic angiography or b-mode ultrasound to distinguish between malignant and non-malignant breast lesions known to exist based on pathological results (the gold standard).

## 3.0 ELIGIBILITY

### 3.1 Inclusion Criteria

Subject must meet all of the inclusion criteria to participate in this study:

3.1.1 Women  $\geq 18$  years old

3.1.2 Scheduled for breast core needle or surgical biopsy of at least one breast lesion based on suspicious breast lesion (BIRADS score of 4 or 5) from pre-study SOC imaging studies

3.1.3 Center of suspicious lesion is not deeper than 1.5 cm.

3.1.4 Able to provide informed consent

3.1.5 Negative urine pregnancy test in women of child-bearing potential

### 3.2 Exclusion Criteria

[figure not shown]
All subjects meeting any of the exclusion criteria at baseline will be excluded from study participation

- 3.2.1 Male (it is uncommon for men to present for imaging and the overwhelming majority of findings are non-cancerous and do not lead to biopsy; male breast cancer represents <1% of newly diagnosed breast cancer)
- 3.2.2 Institutionalized subject (prisoner or nursing home patient)
- 3.2.3 Critically ill or medically unstable and whose critical course during the observation period would be unpredictable (e.g., chronic obstructive pulmonary disease (COPD))
- 3.2.4 Known hypersensitivity to any component of perflutren lipid (Definity®)
- 3.2.5 Right to left shunt, severe pulmonary hypertension (pulmonary artery pressure >90mmHg), or adult respiratory distress syndrome
- 3.2.6 Active cardiac disease including any of the following:
- Severe congestive heart failure (class IV in accordance with the classification of the New York Heart Association)
  - Unstable angina.
  - Severe arrhythmia (i.e. ventricular tachycardia, flutter fibrillation; ventricular premature complexes occurring close to the preceding T-wave, multifocal complexes).
  - Myocardial infarction within 1 year prior to the date of proposed Definity® administration.
  - Uncontrolled systemic hypertension (systolic blood pressure (BP) >150 mm Hg and/or diastolic BP >90 mm Hg despite optimal medical management)
- 3.2.7 Any woman who is pregnant or has reason to believe she is pregnant or any woman who is lactating (the possibility of pregnancy has to be excluded by negative urine  $\beta$ -HCG results, obtained within 24 hours before the perflutren lipid administration, or on the basis of patient history, e.g.: tubal ligation, hysterectomy or a minimum of 1 year without menses)

## 4.0 STUDY PLAN

#### 4.1 Schema

This is a one arm single center study of 60 patients with suspicious breast lesions (BIRADS 4 or 5) from the UNC Breast Clinic that consent to undergo an acoustic angiography in conjunction with b-mode ultrasound prior to their scheduled biopsy.

 Pre-ultrasound contrast agent  
 Based on results of pre-study imaging

#### 4.2 Enrollment/Recruitment

A total of 60 women will be enrolled to this study. The 60 study subjects will be consecutively recruited from women who are scheduled to undergo core needle or surgical biopsy (BIRADS 4 or 5) to have pathological confirmation of malignancy status. Eligible patients will be identified by research staff review in coordination with the UNC Breast Clinic. Once a patient has been referred, the patient will be approached by a coordinator from Radiology to assess interest in participation.

All eligible women who agree to participate in the study will be asked to come to their scheduled biopsy appointment thirty minutes early to complete the informed consent process.

Review of the consent will take place in the privacy of an exam room, or when possible, a sample consent form will be sent to the patient via email prior to the patient's visit to allow for ample review. Once the patient has consented, women of child bearing potential (WCBP) will be given a urine pregnancy test in order to ensure that they are not pregnant. If a urine pregnancy test shows a result positive for pregnancy, the patient will be excluded from the study per the exclusion criteria because the investigators cannot, in good conscience, expose a fetus to the contrast agent used. Women who consent for the study and are eligible will be escorted by the research coordinator to a dressing room, where the subject will change into a gown.

### **4.3 Acoustic Angiography**

#### **4.3.1 Perflutren Administration**

At the time of imaging, the contrast agent perflutren lipid (see section 4.3) will be administered. See

[http://www.definityimaging.com/pdf/VIALMIX\\_Users\\_Guide.pdf](http://www.definityimaging.com/pdf/VIALMIX_Users_Guide.pdf), and the package insert, for instructions on perflutren lipid preparation and activation. Perflutren lipid is intended for intravenous (IV) administration only after activation in the Vialmix® apparatus. Cardiopulmonary resuscitation personnel and equipment will be readily available prior to perflutren administration, and all patients will be monitored for acute reactions.

Perflutren will be administered in a single dose using a bolus administration. (see <http://www.definityimaging.com/how-administration.html>). Although the prescribing information allows for two 10 uL/kg doses separated by 30 minutes, we will be administering double the package recommended dose (administering 20 uL/kg) administered within 30-60 seconds, followed by a 10mL saline flush. No second dose will be administered. All patients will be monitored for 30-minute post-perflutren administration by the research nurse or research physician. Monitoring will include taking vitals (O2 sat, HR, RR, BP). The oxygen saturation, heart rate, and respiration rate will be monitored continuously for 30 min. The blood pressure will be monitored every 15 minutes. This study will be conducted in Mammography of the UNC Cancer Hospital, so trained medical personnel will be available as needed.

The initial concentration will be diluted, although the final dilution amount is not finalized (most likely to range from 1:1 (full dose) to - 1:5 dilution in saline). This dilution technique is still to be determined based on performance because this is a new type of imaging. We will infuse via hand bolus injection. The infusion time will be approximately 30 - 60 seconds for the dose.

#### **4.3.2 Acoustic Angiography Imaging Procedures**

Acoustic angiography imaging involves a research high frequency ultrasound scanner (VisualSonics Vevo 770; see section 5.0) in contrast imaging mode. In addition, we may use a standard FDA-approved clinical ultrasound system to obtain a second conventional B-mode ultrasound image as a gold standard. Imaging will be performed within the package insert guidelines for ultrasound system mechanical index (a measurement of output power) when imaging perflutren contrast agent (less than 0.8).

Acoustic angiography imaging will be performed by a trained medical personnel using mild compression to eliminate motion. A linear translation stage will be attached to the transducer to mechanically translate the

transducer the imaging distance (up to approximately 3 cm). Total imaging time per pass is estimated to be 60 seconds, similar to a standard ultrasonography exam. All image data will be de-identified and transferred for off-line analysis based on a study ID. The research images will NOT be interpreted or analyzed for clinical decisions related to the patient. See section 5.0 for additional information on the acoustic angiography device.

#### 4.4 Standard of Care Biopsy

The patient will then undergo her scheduled breast biopsy procedure based on the pre-study diagnostic imaging. The research acoustic angiography imaging will NOT be interpreted prior to the breast biopsy and therefore will not influence any clinical decision concerning the biopsy.

#### 4.5 Medical Record Abstraction

A secondary objective of this study is to quantify the vessel tortuosity and develop a “model-based malignancy score” to predict malignancy of a lesion based on quantitative tortuosity metrics from the acoustic angiography imaging. In order to meet this objective, we will review each patient’s clinical records, including their pathology report from biopsy. The malignancy will be determined as indicated by the pathology report.

#### 4.6 Reader Study

A total of five readers (radiologists trained in breast imaging) will be recruited to participate in evaluation of all imaging performed under LCCC1405.

In the reader preference study, each reader will be asked to compare the acoustic angiography case to the conventional b-mode ultrasound case to evaluate the imaging characteristics based on the BIRADS ultrasound lexicon

(<http://www.acr.org/~media/ACR/Documents/PDF/QualitySafety/Resources/BIRADS/USLexiconClass.pdf>). Specifically the relative ability to evaluate shape, margins and vascularity will be evaluated using a seven-point scale (-3 to +3) for the paired modality comparisons for each of the 60 cases.

The data collection form for the reader study portion is given in Appendix A, section 13.1.

The readers will be asked to assign a subjective malignancy score (-2 (highly not malignant) to +2 (highly malignant)) and their confidence for each lesion for each modality (0 to 100%). These will also be documented on the form in Appendix A. These scores will be used combined for a binary analysis. Malignancy scores of +1 and +2 will be considered malignant. Scores of -2, -1, and 0 will be considered not malignant. The confidence of malignancy will be used independently in the analysis.

### 5.0 Research Ultrasound Scanner: FUJIFILM VisualSonics Vevo 770

The device used for this study will be a research ultrasound scanner (FUJIFILM VisualSonics Vevo 770) and unique probes developed in conjunction with the research lab run by the founder of VisualSonics, [name]. The ultrasound probes are modifications of Vevo 770 probes (RMV716 probes), modified to house 2 single-element transducers instead of 1.

The Vevo 770 is a research ultrasound system designed for pre-clinical, high resolution imaging of small animals. It is marketed commercially by VisualSonics, Inc., a division of SonoSite, Inc., under the parent company FUJIFILM. This ultrasound system and similar models have been designated to pose no significant risk in other clinical trials by the respective IRBs or other similar regulatory agencies responsible for compliance oversight of these studies. (See section 13.1, Appendix B).

[figure not shown]
[figure not shown]

Figure 1. Device Image

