#### 1.3.1 **Screening Based on Angiogenesis-Acoustic Angiography**

Acoustic angiography allows for the viewing of vessel shape and delineation of 'tortuosity,' which can indicate the presence and progression of cancer. This ability to image the microvasculature depends on the use of a multi (high) frequency ultrasound scanner in addition to a traditional single-frequency pulse-echo ultrasound scanner (b-mode ultrasound), the latter to ensure accurate anatomical location of the lesion. Because of this dependence on pulse-echo, the technique is referred to as "acoustic" angiography [62].

Acoustic angiography also depends on use of an ultrasound contrast agent. Contrast enhanced ultrasound imaging has been used for nearly two decades for clinical cardiology in the United States (and is currently routinely used in UNC Hospital Cardiology Clinics), and is much more widely used in Europe and Asia for visualization of blood perfusion in organs, tissues, and tumors.[51] Early concerns about the safety of ultrasound contrast (specifically with the contrast agent (perflutren lipid; Definity®) due to events in a clinical trial have been resolved; the overwhelming amount of more recent evidence from large clinical studies has shown that contrast ultrasound is very safe.[52-54] In fact ,it is much safer than other commonly used techniques, such as coronary angiography, exercise ECG, or myocardial scintigraphy.[55] Furthermore,

it does not have the risks of nephrogenic systemic fibrosis associated with gadolinium based MRI contrast agents when used in renally compromised patients. On October 27, 2011, the FDA eliminated the requirement for patient monitoring 30 minutes after ultrasound contrast examination, based on these and other recent safety data. The ultrasound contrast agent to be used in LCCC1405 is perflutren lipid.

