### 10.1 Sample Size and Accrual

Per the revision in increased Perflutren dose, we have updated our sample size statistics as follows.

For power calculation, the null hypothesis is that the specificity of acoustic angiography system is the same as the standard of care (b-mode ultrasound), which is assumed to be 70%. (We will determine the specificity of b-mode ultrasound during the trial to confirm that the 70% represents the specificity in the hands of UNC radiologists) Under the alternative, we expect that the specificity of the new device is at least 90%. The specificities are measured relative to pathological diagnosis as the reference standard. With 60 lesions and 5 readers, where we anticipate that roughly half will be malignant, assuming the correlation from the same patient to be 0.5 and the readers to read different patients independently, the power to see specificity at least larger than 90% is 98% at the significance level 0.05 using one-side test. With 50 lesions (half are benign), the power to see specificity of 90% is >96%; with 25 lesions (about 13 are benign), this power becomes 72%. The power to reject the null hypothesis is 98%. Although we will study both sensitivity and specificity, our power calculation is based on specificity, which is the primary interest.

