### 10.2 Data Analysis Plans

#### 10.2.1 Primary Analysis

This is a prospective study to assess the diagnostic performance of the newly developed device. The **primary outcome of interest is the sensitivity and specificity of the acoustic angiography device as compared to b-mode ultrasound**. The sensitivity and specificity can be estimated non-parametrically as the proportion of the lesions which are distinguished as malignant versus non-malignant compared to the reference. This estimate will be calculated for each reader then averaged over all the readers. The standard error of the average sensitivity and specificity estimate will be calculated using the bootstrap method, where each patient is treated as independent unit with 5 ratings. The confidence interval of the final estimate will be provided using the normality assumption.

Furthermore, we will estimate the sensitivity and specificity of the b-mode ultrasound in this study and compare it with the sensitivity and specificity estimate of the acoustic angiography device using the bootstrap approach and the confidence interval of their differences will be provided using the normality assumption.

Malignancy scores of +1 and +2 will be considered malignant. Scores of -2, -1, and 0 will be considered not malignant. The confidence of malignancy will be used independently

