## **11.4 Data Management and Monitoring/Auditing**

The breast images of all eligible enrolled subjects that are obtained and contribute to the ultimate diagnosis leading to biopsy will be de-identified for inclusion in the reader study. Copies of the clinical report forms as well as the de-identified images described in the preceding will be submitted for each case to the Study Coordinators for maintaining the study record and entering the data into a spreadsheet in preparation for the reader study.

As an investigator initiated study, this trial may also be audited by the Lineberger Cancer Center audit committee every twelve months.

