##### ULTRASOUND

Overall specimen malignancy score (-2 to +2): \_\_\_\_\_

Malignancy confidence (0-100) \_\_\_\_\_%

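### Nothing in the plan keeps one modality's read from informing the other, so the primary difference is at risk of bias in an unknown direction

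*Combined protocol and SAP*

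**What the plan says.** Section 4.6 (Reader Study) has five breast radiologists evaluate all study imaging. For the preference part, "each reader will be asked to compare the acoustic angiography case to the conventional b-mode ultrasound case" on shape, margins and vascularity. The same section asks for a malignancy score from -2 to +2 and "their confidence for each lesion for each modality (0 to 100%). These will also be documented on the form in Appendix A".

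Appendix A is a single form with one Specimen, one Reader and one Date field. Its printed order is the acoustic angiography score and confidence, then the ultrasound score and confidence, then three ratings of one modality against the other.

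Section 10.2.1 dichotomises the malignancy scores to give sensitivity and specificity for each modality. For b-mode, the plan is to "compare it with the sensitivity and specificity estimate of the acoustic angiography device using the bootstrap approach". Section 10.1 adds a second use of the b-mode scores: "We will determine the specificity of b-mode ultrasound during the trial to confirm that the 70% represents the specificity".

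On masking, section 4.3.2 says "All image data will be de-identified and transferred for off-line analysis based on a study ID", and section 11.4 says that images "will be de-identified for inclusion in the reader study". On what an acoustic angiography read consists of, section 1.3.1 says the technique uses a high-frequency scanner in addition to conventional b-mode, "the latter to ensure accurate anatomical location of the lesion".

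**The concern.** The primary objective contrasts two modalities, so each score must reflect the modality it is credited to. A b-mode score given after the reader has seen the angiography images of the same lesion no longer measures b-mode alone. If angiography is meant to be read alone, the same holds in reverse.

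The protocol does not say that the reads are simultaneous. It leaves this open, and a reader who fills in the form from top to bottom on one date would comply with it while scoring the comparator second.

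Using the same readers and lesions for both modalities is a sound paired design and is not the fault. The fault is that nothing separates the two reads within each pair, and that the test being evaluated (angiography alone, or angiography with b-mode) is not defined. Without that definition the primary difference has no fixed meaning.

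**Working it through.** **1. Is there a safeguard elsewhere?** The statements that come closest were set against what is needed.

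| Place | What it provides | Does it separate the two reads? |
|---|---|---|
| 4.3.2 and 11.4 | De-identified images | No. It hides the patient, not the other modality |
| 4.4 | Research images not interpreted before biopsy | No. It protects the clinical decision |
| 10.1 | Readers assumed to read different patients independently | No. It concerns patients, not modalities |
| Appendix A | Both malignancy scores printed before the comparative ratings | No. It does not separate the two scores or enforce the order of completion |
| 10.2.1 | Bootstrap with the patient as the unit | No. It acts on the standard error only |

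Sections 4.6, 10.1, 10.2 and 11.4 and Appendix A mention no sessions, washout, reading order, score locking or masking to the other modality.

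**2. The plan's own power figures.** These are not in dispute. Inputs from section 10.1: specificity 70% against 90%, five readers, correlation 0.5, one-sided 0.05.

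- Design effect = 1 + (5 - 1) x 0.5 = 3, so effective n = benign lesions x 5/3.
- Power = Phi[(0.20 - 1.645 x sqrt(0.7 x 0.3/n)) / sqrt(0.9 x 0.1/n)].
- 30 benign: n = 50, power 98.6% (stated 98%).
- 25 benign: n = 41.7, power 96.3% (stated above 96%).
- 13 benign: n = 21.7, power 72.3% (stated 72%).

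The stated figures are reproduced by a one-sample calculation against a fixed 70%. It contains no term for the b-mode read.

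**3. How far could cross-informed reads move the difference?** The documents give no basis for the amount, so the following are illustrations on assumed inputs, using the protocol's 70% and 90%.

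*B-mode copies angiography in a share w of calls (w assumed).* Observed b-mode specificity = 0.70(1 - w) + 0.90w. The observed difference is 0.90 minus that.

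| w | Observed b-mode specificity | Observed difference |
|---|---|---|
| 0 | 70% | 20 points |
| 0.25 | 75% | 15 points |
| 0.5 | 80% | 10 points |

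*Each read borrows from the other in a share c of calls.* The difference becomes 0.20(1 - 2c): 16, 12 and 8 points at c = 0.1, 0.2 and 0.3.

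*The angiography score draws on both images.* Suppose each modality alone has 70% specificity, with independent errors in benign lesions, and the reader calls the angiography case malignant only when both images look malignant. Then specificity = 1 - 0.30 x 0.30 = 91%, an apparent gain of 21 points where angiography alone has none.

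The first two mechanisms shrink the difference and the third creates one. The direction is therefore unknown.

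**4. Can the analysis repair it?** No. Resampling patients with all their ratings carries the correlation between reads into the standard error. A shift already present in the scores is reproduced in every resample.

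**The case against.** The strongest reply is that the point rests on silence. A form records scores; it is not a reading procedure, and a reader manual outside these documents may set one out. The schema figure in section 4.1 is also not visible, though the text governing the reader study is. This stands as a limit: what can be said is that independence of the reads is unspecified, not that the reads are contaminated.

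Second, section 4.6 describes preference and malignancy scoring separately, and the form prints both malignancy scores before the comparative ratings. This weakens the worry that the comparative ratings influence the malignancy scores. It does nothing to keep the two malignancy scores apart.

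Third, the powered hypothesis tests angiography against a fixed 70%. If only the b-mode calls are affected, that test does not change. This is correct for that mechanism. However, sections 2.1 and 10.2.1 make the comparison with b-mode the primary outcome, and a b-mode image that informs the angiography score would shift the angiography estimate too.

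Fourth, sections 1.3.1 and 4.1 describe angiography as used together with b-mode, so part of the influence may be intended. That is fair, but no section defines the test in this way. Even then, the b-mode score would have to be recorded before the angiography images are seen.

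**Conclusion.** The concern holds. Both primary-endpoint scores and the head-to-head ratings share one form, and no provision keeps one modality's read from informing the other. The primary difference in sensitivity and specificity is at risk, as is the in-trial check of the 70% b-mode specificity.

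Neither the size nor the direction of any bias can be derived from the documents. The illustrations show that modest carry-over could take several points off a 20-point difference, and that combined reading could produce a gap of similar size from nothing. They rest on assumed shares of copied calls, or on an assumed combination rule with independent errors, and should carry no more weight than that.

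This should be corrected before reading begins, because an informed score cannot be made uninformed afterwards. Confidence is medium, since an unstated reading procedure may exist.

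**What to change.** In section 4.6, state first whether acoustic angiography is read alone or together with b-mode. Split Appendix A into a b-mode form, an acoustic angiography form and a preference form. Then:

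- **If angiography is read alone:** use separate sessions for each modality with a stated washout, randomise modality order by reader and lesion order within session, and lock each score before the other modality is opened.
- **If angiography is read with b-mode:** obtain and lock an unaided b-mode score before any angiography image of that lesion is shown, and describe the primary comparison as combined reading against b-mode alone.
- **In both cases:** complete the preference form last.

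If separate reads are already intended, a few sentences and the split form are enough.

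The cost is form redesign and additional reading time for the same five readers. The number of malignancy scores stays at 5 x 60 x 2 = 600. With separate sessions, both image sets must be reopened for the 5 x 60 = 300 preference forms, and the washout has to fit within the planned study duration of about two years. No extra patients, readers or imaging are needed, and the power figures in section 10.1 do not change.

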#### *Hypersensitivity Reactions*

The real risk of perflutren in our study is to the small number of potential patients with undiagnosed allergy to perflutren. Post-marketing reports have included anaphylactoid events and other serious but non-fatal adverse reactions, typically within 30 minutes of drug administration (see the package insert, and section 6.1.5 for additional information. In order to avoid a potentially fatal event, EpiPen® (epinephrine) injections will be kept near the US machine for all patients.

*High Ultrasound Mechanical Index (MI)*

High ultrasound MI values may cause microsphere cavitation or rupture and lead to ventricular arrhythmias. In addition, end-systolic triggering with high mechanical indices has been reported to cause ventricular arrhythmias.

*Use in Patients with Known Breast Lesions*

US contrast agents including perflutren should carry no additional risks in patients with a known breast lesions, as they are cleared by the lungs. The phospholipid component of perflutren lipid microspheres are thought to be metabolized to free fatty acids, while the octafluoropropane (OFP), as a stable gas, is not metabolized. In a small (n=8) pharmacokinetic study in healthy subjects, OFP was undetectable after 10 minutes in most subjects either in the blood or expired air, with a mean half-life of 1.3 minutes (Definity® Prescribing Information) .

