#### Overall Assessment:

##### Acoustic Angiography

Overall specimen malignancy score (-2 to +2): \_\_\_\_\_

Malignancy confidence (0-100) \_\_\_\_\_%

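### The reader form has no entry for an unreadable scan, and the midpoint score counts as not malignant, so failed acoustic angiography scans scored 0 would raise the device's specificity

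*Combined protocol and SAP*

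**What the plan says.** Section 4.6 has five breast radiologists who "will be recruited to participate in evaluation of all imaging performed under LCCC1405". The Appendix A form asks, for each modality, for an "Overall specimen malignancy score (-2 to +2") and a confidence percentage. It has no non-diagnostic entry and no image-quality field.

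Section 4.6 makes the score binary: "Scores of -2, -1, and 0 will be considered not malignant". Section 10.2.1 repeats the rule for the primary analysis with no exception: "Malignancy scores of +1 and +2 will be considered malignant. Scores of -2, -1, and 0 will be considered not malignant". Specificity and sensitivity are proportions correct against pathology, computed per reader and then averaged. The bootstrap takes each patient as a unit with five ratings. Sections 4.6 and 10.2.2 are written for 60 readable cases. Section 10 defines no evaluable set and gives no rule for failed, partial or missing images.

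On image acquisition, section 4.3.1 gives one contrast bolus and adds "No second dose will be administered". It also leaves the dilution open because the technique is new. Section 4.3.2 says "Total imaging time per pass is estimated to be 60 seconds" and does not state how many passes are made. Section 1.4.2 cites a small study in healthy subjects in which the contrast gas was cleared "with a mean half-life of 1.3 minutes". Section 4.3.2 also says "we may use a standard FDA-approved clinical ultrasound system to obtain a second conventional B-mode ultrasound image"; that image is optional and is described as a gold standard.

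**The concern.** A reader with nothing to interpret has no way to say so on the form. The midpoint is a natural entry for someone without information, and the cut places it on the negative side. A 0 given for lack of an image is therefore a correct reading when the lesion is benign and an incorrect one when it is malignant. Once entered, it looks the same as a 0 given after a full reading, so no later analysis of the form can separate the two.

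The form and the cut are the same for both modalities, so failures that are equally common on each would largely cancel in the difference. An excess on acoustic angiography would not cancel. Such an excess is plausible: the scanner was designed for small animals, the probes are modified, the dilution is not settled, and the image depends on a single bolus, whereas b-mode needs no contrast.

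Section 10.1 calls specificity the primary interest and bases the power calculation on it alone. Device failures in benign lesions could thus count in favour of the device on the endpoint that drives the design.

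**Working it through.** **Inputs from the documents.** Null specificity 0.70, alternative 0.90, 60 lesions with about half benign (30), 5 readers, correlation 0.5 within a patient, one-sided 0.05 (section 10.1). B-mode sensitivity 0.96 (section 1.2), used only as an illustration. **Assumption.** The documents give no failure rate; f, the excess share of failed angiography scans, is set at 10% and 20%.

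**1. The plan's own power.** Effective number of benign readings: n_eff = n_benign × 5 / (1 + 4 × 0.5). Power = Φ[(0.20 − 1.645·√(0.7×0.3/n_eff)) / √(0.9×0.1/n_eff)].

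| Lesions | Benign | n_eff | Computed | Stated |
|---|---|---|---|---|
| 60 | 30 | 50 | 98.6% | 98% |
| 50 | 25 | 41.7 | 96.3% | >96% |
| 25 | 13 | 21.7 | 72.3% | 72% |

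The stated figures are reproduced. They allow for fewer lesions but are not tied to unreadable scans.

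**2. Failures scored 0 by all readers.** Observed specificity = f + (1 − f)·s; observed sensitivity = (1 − f)·sens.

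- f = 10%: specificity 0.10 + 0.90×0.70 = 73%; sensitivity 0.90×0.96 = 86.4%.
- f = 20%: specificity 0.20 + 0.80×0.70 = 76%; sensitivity 0.80×0.96 = 76.8%.

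The bias in specificity is f·(1 − s), that is +3 and +6 points.

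**3. False-positive rate of the paired comparison.** Both modalities truly 70% specific, 30 benign lesions, 5 readers, between-reader correlation 0.5, b-mode never failing, one-sided 5% test of the difference:

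| Model | f = 0 | f = 10% | f = 20% |
|---|---|---|---|
| Latent normal, modalities uncorrelated | 5.7% | 10.8% | 18.4% |
| Latent normal, between-modality lesion correlation 0.5 | 5.6% | 11.9% | 22.0% |
| Beta-binomial, modalities independent | 5.7% | 11.1% | 18.6% |

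Section 10.2.1 does not state the confidence level for the difference. If the criterion were a two-sided 95% interval lying above zero, the beta-binomial model gives 3.2%, 6.5% and 11.9%.

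**4. Failures dropped.** If they are dropped at random, specificity stays at 70%, and power at 90% is 97.5% (27 benign lesions) or 95.6% (24). Bias needs a link with difficulty. With 70% overall and 50% among the failed lesions, dropping 10% gives (0.70 − 0.10×0.50)/0.90 = 72.2%, and dropping 20% gives (0.70 − 0.20×0.50)/0.80 = 75%.

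**5. Failures counted as incorrect.** Observed specificity = (1 − f)·s. A true 90% becomes 81% at f = 10% and 72% at f = 20%. One-sample power by the formula in step 1 falls from about 98% to 52% and 9%.

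**6. Time for another pass.** With a half-life of 1.3 minutes (78 seconds), 0.5^(60/78) = 59% of the agent remains after one 60-second pass.

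**The case against.** The documents nowhere say that an unreadable scan is scored 0. A reader could enter any value. Every lesion is BIRADS 4 or 5, so a cautious +1 is possible, and it would lower specificity. This stands: the direction of the bias depends on reader behaviour that the plan leaves open. It does not remove the gap, because the result would then rest on a habit that the form does not record.

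A reader might infer that a failed scan cannot be repeated. The text bars a second dose, not a second pass, and section 5.2 allows 15 minutes of imaging. The half-life comes from blood and expired air in eight healthy subjects and is not an imaging window. What remains is that time for another pass under the same bolus is probably limited.

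A reader might also infer that dropping failures inflates specificity. Step 4 shows that this happens only if failure is related to lesion difficulty. Dropping them from one modality alone would, however, break the pairing.

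The gain in specificity is not free, since sensitivity is also part of the primary outcome and would fall. That is correct, but no power calculation is attached to sensitivity.

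Finally, it would go too far to say that failures are never recorded. The plan refers to other case report forms that are not included; only the reader form can be judged.

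**Conclusion.** The gap is real and bears on the powered endpoint. The form has no place for an unreadable scan, the cut makes a midpoint entry correct for every benign lesion, and the two kinds of 0 cannot be separated afterwards.

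The size is +3 points of specificity at 10% excess failure and +6 at 20%, with the one-sided false-positive rate rising from about 6% to about 11-12% or 18-22%. This rests on assumed failure rates, on all five readers scoring every failed scan 0, and on true specificity of 70% on both modalities. With fewer failures, or with failures as common on b-mode, the effect on the comparison is smaller.

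A larger figure is tempting. The distance between scoring failures 0 and counting them incorrect is 10 points at f = 10% (73% against 63%) and 20 at f = 20% (76% against 56%). Most of that distance is the penalty in the second rule, not bias in the plan, and it should not be quoted as the error.

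**What to change.** - **Appendix A:** add a non-diagnostic box for each modality, and instruct readers not to use 0 for a scan they cannot read.
- **Section 10.2.1:** compare the modalities on the same set of lesions, and report non-diagnostic counts by modality and by pathology.
- **Two analyses:** give sensitivity and specificity on the lesions readable on both modalities, and again with non-diagnostic reads counted as incorrect. State before reading starts which is primary. Either choice can be defended; what matters is that it is made without sight of the scores.

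The cost is a small form change, a sentence of reader instruction and one extra analysis. No dose, visit or procedure changes. The consequence for the result is not trivial: if failures counted as incorrect is made primary, a device with true 90% specificity would show 81% at 10% failure, with one-sample power of about 52%. The team should weigh this when choosing the primary analysis.
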